СМН	Cochran-Mantel-Haenzel
EMA	European Medicines Agency
FAS	Full Analysis Set
IDMC	Independent Data Monitoring Committee
IRT	Interactive response technology
ITP	Immune thrombocytopenia
IVIg	Intravenous immune globulin
MedDRA	Medical Dictionary for Regulatory Activities
PD	Pharmacodynamic
PIP	Paediatric Investigation Plan
PK	Pharmacokinetic
PPS	Per-protocol analysis set
PT	Preferred Term
Q1	First Quartile
Q3	Third Quartile
SAE	Serious adverse event
SD	Standard deviation
SOC	System organ class
TEAE	Treatment emergent adverse event
TPO	Thrombopoietin
TPO-RA	Thrombopoietin receptor agonist
US	United States
WHO	World Health Organization

1. INTRODUCTION

This statistical analysis plan is designed to outline the statistical methods for study AVA-PED-301 to evaluate the efficacy, safety, tolerability, and PK/PD profile of avatrombopag, as well as provide data on palatability/acceptability, dosing parameters, and response to treatment.

This document has been prepared based on protocol version 3.0 dated 02Nov2021 and Case Report Form (CRF) dated 10Jan2023.

Analysis for PK/PD will be addressed in a separate statistical analysis plan.

2. STUDY DESIGN

2.1 Summary of Study Design

AVA-PED-301 is a multi-center, randomized, double-blind, placebo-controlled, parallel-group study in pediatric subjects with a 12 week Core Phase followed by a 2-year open-label Extension Phase to evaluate the efficacy, safety, tolerability, and PK/PD profile of avatrombopag, as well as to provide data on palatability/acceptability, dosing parameters, and response to treatment.

The study will enroll at least 72 pediatric subjects, aged ≥ 1 to <18 years (Figure 1). Subjects will be assigned to 3 age cohorts in a 2:2:1 ratio and subjects will be randomized within each cohort in a 3:1 ratio to receive either avatrombopag or placebo. Subject age at the time of randomization will be used. Cohort 1 and Cohort 2 will each enroll more subjects than will be enrolled in Cohort 3 in order to minimize the exposure of the youngest age group to placebo. Randomization will be stratified by age cohort. Subjects will also be stratified by an average baseline platelet count of $\leq 15 \times 10^9/L$ or $>15 \times 10^9/L$ to $<30 \times 10^9/L$ in order to ensure treatment groups are approximately balanced.

[figure not shown]
Enrollment into the Core Phase will be staggered by descending age cohort.

- Cohort 1: \ge 12 to \le 18 years (n = 21 avatrombopag; 7 placebo)
- Cohort 2: \geq 6 to <12 years (n = 21 avatrombopag; 7 placebo)
- Cohort 3: ≥ 1 to ≤ 6 years (n = 12 avatrombopag; 4 placebo)

All available PK and safety data through Week 10 of the Core Phase will be reviewed by the Sponsor and/or the Sponsor's designee (e.g., for unblinded PK data) for the first 10 subjects enrolled into Cohort 1 prior to opening enrollment into the Core Phase for subjects in Cohort 2. Likewise, all available PK and safety data through Week 10 will be reviewed by the Sponsor and/or the Sponsor's designee (e.g., for unblinded PK data) for the first 10 subjects enrolled into Cohort 2, prior to opening enrollment into the Core Phase for Cohort 3. As the study progresses and more data become available, the PK/PD model will be updated with emerging data in order to confirm the appropriate dose of avatrombopag in each cohort. Enrollment will not stop in the current cohort for the data review after Week 10, or for the data review after each cohort is fully enrolled. The dose of avatrombopag may be modified during the study based on results of the PK and safety data

review. In addition, safety data will be reviewed on an ongoing basis and new enrollment may be paused for any serious unexpected and related AEs that occur.

Figure 1: AVA-PED-301 Study Design

^{*}Dose titration based on platelet count.

In order to minimize the number of blood draws subjects are subjected to, blood samples for *serial* PK assessments will only be collected during Visit 4 (Week 2) and Visit 12 (Week 10) of the 12 week Core Phase. For all age groups, blood samples for *sparse* PK assessments (2 mL each) will be collected while the subject is at the clinic during Visit 3 (Week 1) and at each weekly visit during the period from Visit 5 (Week 3) to Visit 11 (Week 9) (there will be 8 total PK samples drawn across these visits, 2 mL each). This frequency of sparse and serial PK blood sampling will allow for a comparison of PK values between pediatric and adult ITP patients and to confirm the appropriate dose of avatrombopag prior to opening the next cohort for enrollment.

Subjects who are not showing a platelet response (i.e., a lack of treatment effect) at the highest dose of study drug based on the subject's age cohort may be terminated from the Core Phase and directly enrolled into the open-label Extension Phase.

Lack of treatment effect will be defined as:

- Platelet count remains <30×10⁹/L after more than 3 weeks at the maximum dose of study drug per cohort. Subjects may also be terminated from the Core Phase and directly enrolled into the Extension Phase after 7 days of therapy at the maximum dose if they have dangerously low platelet counts (in the opinion of the Investigator), or
- Subjects who require rescue therapy more than 3 times or continuous rescue therapy for more than 3 weeks.

The Core Phase of the study will last 12 weeks (approximately 84 days), which does not include the 4 week Follow-up Period, with study visits occurring once weekly through the end of Week 12.

Subjects who complete the 12 week Core Phase of the study, or who meet the stopping criteria and are discontinued from the Core Phase, will be eligible to enter the open-label Extension Phase, if they continue to meet the inclusion criteria and do not meet any exclusion criteria for this phase of the study. The Extension Phase of the study will last 2 years during which time the subject will have monthly clinic visits. Subjects may be early terminated from the Extension Phase if they have a platelet count $>250\times10^9$ /L after 2 weeks of once weekly dosing for any age cohort or if they have a platelet count $<30\times10^9$ /L after 3 weeks of once daily dosing at the cohort defined maximum dose.

2.2 Sample Size Determination

The proposed sample size is based on the anticipated response rates for avatrombopag and placebo for the primary endpoint (durable response) and the key secondary endpoint (platelet response for 2 consecutive weeks).

Based on the eltrombopag PETIT2 study conducted in pediatric patients with chronic ITP, the durable response rates were 41.3% and 3.4% for eltrombopag and placebo, respectively (Grainger, 2015). It is reasonable to assume that the treatment effect of avatrombopag will be very similar to that of eltrombopag, due to both drugs being in the same class, having similar mechanisms of action, and treating similar patient populations (e.g., patients aged ≥ 1 to <18 years with relapsed or refractory disease after 1 or more previous treatments for ITP and a Baseline platelet count $<30\times10^9$ /L). With the 3:1 ratio of avatrombopag to placebo, a total of 72 subjects (54 avatrombopag and 18 placebo) will provide at least 90% power to detect a treatment difference of 37.9% in durable response at α =0.05, based on the Fisher's exact test.

In addition, a 12 week study of romiplostim in treating pediatric ITP patients showed that 88% of romiplostim treated subjects achieved a platelet count $\geq 50 \times 10^9 / L$ for 2 consecutive weeks (key secondary endpoint), whereas none of the placebo treated subjects achieved the same endpoint (Bussel, 2011). With the 3:1 ratio of avatrombopag to placebo, a total of 72 subjects (54 avatrombopag and 18 placebo) will provide $\geq 99\%$ power to detect a treatment difference of 80% in proportion of subjects achieving a platelet count $\geq 50 \times 10^9 / L$ for 2 consecutive weeks at $\alpha = 0.05$, based on the Fisher's exact test.

2.3 Randomization and Blinding

During Day 1/Visit 2 of the Core Phase, after study eligibility has been confirmed, randomization assignment will be performed using interactive response technology (IRT). Randomization will be stratified by age cohort. Subjects will also be stratified by a baseline platelet count of $\leq 15 \times 10^9/L$ or $>15 \times 10^9/L$ to $<30 \times 10^9/L$ in order to ensure treatment groups are approximately balanced. Following randomization, study drug will be dispensed in a double-blind manner. The Sponsor, the subject, and the clinical site personnel will be blinded to the treatment assignment.

No randomization or blinding is necessary for the Extension Phase as all subjects will receive open-label avatrombopag.

3. STUDY OBJECTIVES AND ENDPOINTS

3.1 Study Objectives

• Primary Objective

- to demonstrate that the efficacy of avatrombopag is superior to placebo for the treatment of pediatric subjects with ITP of ≥ 6 months duration who have had an insufficient response to a previous treatment

• Secondary Objectives

- to evaluate the safety and tolerability of avatrombopag
- to evaluate the PK and PD of avatrombopag

• Exploratory Objective

 to provide data on the palatability and parent/caregiver reported acceptability of the avatrombopag powder for oral suspension

3.2 Study Endpoints

3.2.1 Efficacy Endpoints

• Primary Efficacy Endpoint

Durable platelet response defined as the proportion of subjects achieving at least 6 out of 8 weekly platelet counts ≥50×10⁹/L during the last 8 weeks of the 12 week Treatment Period in the Core Phase in the absence of rescue medication

• Alternative Primary Efficacy Endpoint (per EMA PIP)

Platelet response as defined by the proportion of subjects for whom at least 2 consecutive platelet assessments are ≥50×10⁹/L over the 12 week Treatment Period in the Core Phase in the absence of rescue medication

Additional Secondary Efficacy Endpoints

- The percentage of weeks subjects have a platelet count ≥50×10⁹/L during 12 weeks of treatment in the Core Phase, in the absence of rescue therapy.
- Platelet response at Day 8 (defined by the proportion of subjects with a platelet count $\geq 50 \times 10^9$ /L at Day 8, in the absence of rescue therapy).
- The percentage of weeks subjects have a platelet count between ≥50×10⁹/L and ≤150×10⁹/L, during 12 weeks of treatment in the Core Phase, in the absence of rescue therapy.
- The proportion of subjects who require rescue medications during 12 weeks of treatment in the Core Phase of the study.
- Incidence and severity of bleeding symptoms associated with ITP measured using the WHO Bleeding Scale

3.2.2 Safety Endpoints

- Incidence of AEs, SAEs, and AEs of special interest (AESI) during the study
- Measurement of clinical laboratory tests during the study
- Measurement of vital signs during the study

3.2.3 Exploratory Endpoints

- Platelet count assessments and platelet response during the Extension Phase
- Subject reported palatability and parent/caregiver reported acceptability assessed by a
 palatability/acceptability questionnaire administered after the first dose of the powder for
 oral suspension
- Month 3 durable platelet response defined as the proportion of subjects achieving at least 3 out of 4 weekly platelet counts $\geq 50 \times 10^9 / L$ during the last 4 weeks of the 12 week Treatment Period in the Core Phase in the absence of rescue medication

4. DEFINITIONS AND CONVENTIONS FOR DATA HANDLING

4.1 Study Periods

Study periods are defined as follows:

Screening Period: Starting the day of signature of informed consent up to and including the day before randomization. For subjects who are not randomized, the screening period will end on the day the subject is determined to be a screen failure.

Randomized Control Period / **Core Phase**: Starting the day of randomization up to Visit 14 or the day of study drug discontinuation.

Follow-up Period in Core Phase: Starting the day after last dose of study drug in the Core Phase up to 30 days (±7 days) following the last dose of study drug in the Core Phase (only for subjects not entering the open label extension period).

Open Label Extension Period: Starting the day of Visit E-1/Day 1 to early termination or end of study. Visit 14 and Visit E-1 occur on the same day, and as a result are part of both the Randomized Control Period and the Open Label Extension Period.

4.2 Visit Windows

No formal visit windowing will be conducted. Only the scheduled visit assessments will be used in the by-visit analyses. If multiple records are found within the visit window, the record closest to target date will be used for analysis purposes. If two records with equal distance to the target date, the average value of the two records will be used for analysis. The exceptions are for analyses of the worst post-baseline or all post-baselines; both scheduled and unscheduled visit assessments will

be used for these analyses. Additionally, records of the End of Study visit will be assigned to the appropriate visit per the study day.

4.3 Definition of Baseline

4.3.1 Baseline Platelet Count

In the efficacy analysis, baseline platelet count is the average of the platelet count obtained at the Screening Visit/Visit 1 and 1 other platelet count taken within 28 days on either side of the Screening Visit (may use a historical value collected per standard of care if within 28 days of the Screening Visit). The 2 samples must be obtained \geq 24 hours and \leq 28 days apart and the results must be available prior to randomization. This baseline platelet count will also be used as the stratification factor.

In the safety analysis, baseline platelet count is defined as the most recent non-missing measurement prior to first dose date/time of study drug in randomized control period.

4.3.2 Baseline for Other Evaluations

For all other evaluations (except WHO bleeding scale), baseline is defined as the most recent non-missing measurement prior to first dose date/time of study drug in the randomized control period.

For WHO bleeding scale, baseline is defined as the most severe (worst) bleeding event recorded prior to the first dose date/time of study drug in the randomized control period.

Grade 0	No bleeding
Grade 1	Petechial bleeding
Grade 2	Mild blood loss (clinically significant)
Grade 3	Gross blood loss
Grade 4	Debilitating blood loss

4.4 Definition of Study Days

Unless otherwise noted, study days of an evaluation are defined as number of days relative to the first dose date in each study phase.

• If evaluation date is on or after first dose date, then study days are calculated as

Evaluation date - first dose date + 1

• If evaluation date is before first dose date, then relative study days are calculated as

Evaluation date - first dose date

4.5 Handling Rules for Platelet Counts

Platelet counts are collected at local laboratories for eligibility and efficacy assessments. Platelet count is also included in the hematology panel sent to the central laboratory as a safety evaluation. For the efficacy analyses, only platelet counts assessed by the local laboratories will be included in

the calculations and summaries. For the safety analyses, only platelet counts assessed by the central laboratory will be included in the summaries.

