- Collect blood for platelet count (local laboratory).
- Determine appropriate Extension Phase starting dose of open-label avatrombopag per the instructions in Section 1.1.6.

- Retrieve unused study drug from the Core Phase and record compliance in the eCRF.
- Dispense new Dosing Diary for the subject to take home with instructions for completion.
- Dispense 1-month supply of open-label avatrombopag for the subject to take at-home with instructions for administration.
- Review study drug administration and Dosing Diary completion with the subject and/or the subject's caregiver.
- Record any AEs.
- Review and record any concomitant medications, including any modifications to or new concomitant ITP medications.
- Discharge subject from clinic with instructions for when to return for Visit E-2/Month 2 (Section 9.1.19).

For subjects who are not continuing into the Extension Phase, Visit 14 should be completed and Visit 15 (Section 9.1.16) will be the last study visit.

Procedures to Complete during Visit 14/Visit E-1 if the Subject is NOT Continuing into the Open-label Extension Phase:

- Perform WHO Bleeding Scale Assessment (Appendix C). The Investigator should ask the subject and/or the subject's parent/caregiver the following question: "Have you had any bleeding or bruising since I saw you last?". This assessment should be completed prior to other visit assessments.
- Perform abbreviated PE. The abbreviated PE will consist of the following: general appearance, head, neck, eyes, ears, nose, throat, chest, lungs, heart, abdomen, extremities, joints, lymph nodes, and neurology.
- Collect height and weight to determine BMI (calculated by eCRF).
- Collect vital signs (blood pressure, heart rate, and temperature). Vital signs should be taken after sitting for 5 minutes, whenever possible, and prior to any blood draws.
- Collect blood for clinical laboratory tests (e.g., serum chemistry, hematology [Table 7]).
- Collect blood for platelet count (local laboratory).
- Perform urine or serum pregnancy test for female subjects of childbearing potential. The pregnancy test may be performed locally.
- Retrieve unused study drug and record compliance in the eCRF.
- Record any AEs.
- Review and record any concomitant medications, including any modifications to or new concomitant ITP medications.
- Discharge subject from clinic with instructions for when to return for Visit 15.

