9.2.4 Visit E-25/End of Study Visit – Extension Phase

The Extension Phase End of Study Visit should be performed 30 days (±7 days) after Visit E-24.

The following assessments will be performed during the Extension Phase End of Study Visit.

- Perform WHO Bleeding Scale Assessment (Appendix C). The Investigator should ask the subject the following question: "Have you had any bleeding or bruising since I saw you last?". This assessment should be completed prior to other visit assessments.
- Perform abbreviated PE. The abbreviated PE will consist of the following: general appearance, head, neck, eyes, ears, nose, throat, chest, lungs, heart, abdomen, extremities, joints, lymph nodes, and neurology.

- Collect vital signs (blood pressure, heart rate, and temperature). Vital signs should be taken after sitting for 5 minutes, whenever possible, and prior to any blood draws.
- Collect blood for platelet count (local laboratory).
- Perform urine or serum pregnancy test for female subjects of childbearing potential. The pregnancy test may be performed locally.
- Retrieve unused study drug and record compliance in the eCRF.
- Record any AEs.
- Review and record any concomitant medications, including any modifications to concomitant ITP medications.
- Discharge subject from the study.

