9.3 Early Termination Assessments

Should the subject early terminate from the study, the following assessments should be performed if possible.

- Perform WHO Bleeding Scale Assessment (Appendix C). The Investigator should ask the subject the following question: "Have you had any bleeding or bruising since I saw you last?".
- Perform abbreviated PE. The abbreviated PE will consist of the following: general appearance, head, neck, eyes, ears, nose, throat, chest, lungs, heart, abdomen, extremities, joints, lymph nodes, and neurology.
- Collect vital signs (blood pressure, heart rate, respiratory rate, and temperature). Vital signs should be taken after sitting for 5 minutes whenever possible and prior to any blood draw.
- Collect blood and urine for clinical laboratory tests (e.g., serum chemistry, hematology, and urine pregnancy test).
- Collect blood for platelet count (local laboratory).
- If a subject is early terminated from the study prior to the end of the PK blood draw collection in Visit 10 of the Core Phase, consideration should be given to collecting all remaining PK blood draws prior to discharging from the study.
- Record any AEs.
- Review and record any concomitant medications.
- Collect unused study drug and completed Dosing Diary.
- Discharge subject from study.

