bb For subjects who are early terminating from the study, only. Final study drug collection will occur at Visit 14 for subjects who have completed the Core Phase.

cc Adverse events (AEs) should be recorded from the time the subject/subject's legally authorized representative (LAR) signs the informed consent/assent.

Table 8 AVA-PED-301 – Extension Phase Schedule of Events

Visit	E-1 ^a	E-2	E-3	E-4	E-5	E-6	E-7 – E-24	E-25
Day	1	30 (±7 Days)	60 (±7 Days)	90 (±7 Days)	120 (±7 Days)	150 (±7 Days)	Every 30 Days (±7 Days)	720 (±7 Days)
Informed Consent/Assent ^b	X							
Inclusion/Exclusion Criteria Review	X							
WHO Bleeding Scale ^c	X	X	X	X	X	X	X	X
Vital Signs ^d	X							X
Height, Weight, BMI	X	Xe	Xe	Xe	Xe	Xe	Xe	
Abbreviated Physical Exam ^f	X			X			Xg	X
Serum Chemistry/Hematology (Central Lab)	X							
Platelet Count (Local Lab)h	X	X	X	X	X	X	X	X
Pregnancy Test ⁱ	X		X			X	X	X
Determine Appropriate Starting Dose/Assess need for Dose Titration	X	X	X	X	X	X	Х	
Administer Avatrombopag in Clinic ^j	X					X	X	
Dispense 1-month Supply of Open-label Avatrombopag	X	X	X	X	X	X	X	

BMI = Body Mass Index

^a Visit E-1 will be the first visit of the Extension Phase and the last Visit of the Core Phase (Visit 14).

^b Informed consent/assent may be performed at any time during the Core Phase for the Extension Phase.

^c WHO = World Health Organization. The following question should be asked of the subject during each visit: "Have you experienced any bruising or bleeding since I saw you last?".

^d Vital signs (blood pressure, heart rate, respiratory rate, and temperature) should be taken after sitting for 5 minutes, whenever possible. Vital signs should also be taken prior to any blood draws.

^e Weight only.

^f The abbreviated physical exam (PE) will consist of the following: general appearance, head, neck, eyes, ears, nose, throat, chest, lungs, heart, abdomen, extremities, joints, lymph nodes, and neurology.

g The abbreviated PE should be performed every 3 months while the subject is enrolled in the extension phase (e.g., Day 90, Day 180, Day 270, Day 360, Day 450, Day 540, Day 630, and Day 720).

h Platelet counts are to be assessed weekly until the subject is determined to be on a stable dose of avatrombopag. Record weekly visits, dose changes, and platelet counts on the electronic case report form (eCRF).

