7.5.3 Clinical Laboratory Tests

Observed and changes from baseline for clinical laboratory (serum chemistry and hematology) parameters will be summarized (based on Section 7.1) by visit for Safety Analysis Set in the Core Phase. Observed values for clinical laboratory (serum chemistry and hematology) parameters will be summarized by visit for Safety Analysis Set in the Extension Phase.

Number and percentage of subjects with abnormal values will be tabulated by visit for applicable parameters.

Platelet count results from the central lab will be used in the safety assessments of clinical laboratory tests.

Laboratory results will be listed for the Safety Analysis Set.

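### Safety summaries of platelet count admit only central-laboratory values, none of which is scheduled after Extension Visit E-1, and no planned table counts subjects above 250×10⁹/L

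*SAP*

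**What the plan says.** SAP 4.5 assigns local-laboratory platelet counts to efficacy and then rules: "For the safety analyses, only platelet counts assessed by the central laboratory will be included in the summaries". SAP 7.5.3 names the central laboratory again as the platelet source for the safety assessment. It plans that observed chemistry and hematology "parameters will be summarized by visit for Safety Analysis Set in the Extension Phase", and adds: "Number and percentage of subjects with abnormal values will be tabulated by visit for applicable parameters".

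The schedule supplies little central data to these outputs:

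- In Protocol Table 8 the row "Serum Chemistry/Hematology (Central Lab" is marked at E-1 only, while the local platelet row is marked at every visit.
- SAP 4.1 notes that "Visit 14 and Visit E-1 occur on the same day" and places that visit in both periods. Protocol 9.1.15 lists the laboratory draw ahead of the step "Determine appropriate Extension Phase starting dose of open-label avatrombopag".
- Protocol 9.2.3 (E-2 to E-24) lists a local platelet count and no chemistry or hematology. Protocol 9.2.4 (E-25) does the same: "Collect blood for platelet count (local laboratory".
- The exception is early termination, in Protocol 9.3: "Collect blood and urine for clinical laboratory tests (e.g., serum chemistry, hematology, and urine pregnancy test".

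Local counts are reported under efficacy. SAP 7.4 summarizes them by visit in both phases and lists them for the Full Analysis Set, and SAP 7.1 includes the maximum among the descriptive statistics. SAP 4.2 restricts by-visit analyses to scheduled assessments. It lets unscheduled values into analyses of the worst or of all post-baseline values.

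**The concern.** A TPO-receptor agonist is titrated on platelet count, and Protocol Table 3 stops study drug and increases monitoring to twice weekly when the count exceeds 250×10⁹/L. Thromboembolic events are an adverse event of special interest. How many subjects passed the protocol's own stop-drug level is therefore a basic descriptive safety fact. The data to answer it are collected, but SAP 4.5 keeps them out of the safety summaries and no other planned table gives the number.

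What is at stake is the completeness of the safety report. In a 2-year extension, the safety summary of platelet count would show E-1 and whatever early-termination samples exist. For subjects randomized to placebo, no central count is scheduled while they are taking avatrombopag.

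**Working it through.** This is a count from the two schedules of events. No model is involved.

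**The plan's own figure.** Protocol 9.5 expects 24 Extension blood draws. E-2 to E-25 gives 25 − 1 = 24, which fits a reading in which E-1 is counted in the Core Phase. E-1 to E-24 also gives 24, and the figure leaves out the weekly counts taken until the dose is stable. The agreement is consistent with Table 8 but is not proof of it. Protocol 9.2.3 and 9.2.4 are the better confirmation, because both list a local count and no central panel.

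**Extension Phase (Table 8).**
- Visits E-1 to E-25: 25.
- Visits with scheduled central hematology: 1 (E-1), so 1/25 = 4%.
- After E-1: 0 scheduled central counts and 24 scheduled monthly local counts per subject who completes.
- Local counts beyond those 24: weekly until the dose is stable (Protocol 9.2.3 and Table 8) and twice weekly after a count above 250×10⁹/L (Table 3). The documents do not allow these to be numbered.
- Planned placebo subjects: 18. Their E-1 sample is the Visit 14 sample and is listed before the open-label dose is set. Scheduled central counts on avatrombopag: 0 per subject.

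**Core Phase (Table 7).**
- On-treatment weekly local counts, Weeks 1 to 12: 12.
- Weeks with central hematology: 4, 8 and 12, so 3/12 = 25%. The other 12 − 3 = 9 weekly counts cannot enter a safety summary under SAP 4.5.

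**Does another planned output give the number of subjects above 250×10⁹/L?**

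| Output | Why it does not |
|---|---|
| Abnormal-value table (SAP 7.5.3) | Central values only; 250 lies inside the normal range of 150 to 450×10⁹/L in Protocol 1.1 |
| By-visit platelet summaries (SAP 7.4) | Give a maximum per visit, not a number of subjects; scheduled visits only |
| Percentage-of-weeks endpoints (SAP 7.4) | Core only; the difference between the two gives weeks above 150, not above 250 |
| TEAEs leading to dose reduction or interruption (SAP 7.5.2) | Only events recorded as AEs; for laboratory findings that is the investigator's judgment (Protocol 10.1) |
| Disposition (SAP 7.2.2) | Discontinuations only; holds and reductions do not appear, and the reason categories are not listed |
| Platelet listing (SAP 7.4) | Would have to be counted by hand |

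Planned tables that give the number: 0. The SAP 4.2 provision for worst post-baseline values would allow one, but neither SAP 7.4 nor SAP 7.5.3 specifies such a platelet analysis.

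**If local counts were admitted.** Scheduled coverage would rise from 1 of 25 to 25 of 25 Extension visits, and from 3 of 12 to 12 of 12 on-treatment Core weeks, with unscheduled counts in addition.

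**The case against.** The best case for the plan is that little is hidden. Local counts are summarized by visit with maxima and are listed, and several other outputs carry related information. AESI reporting, laboratory AEs and IDMC review cover clinical consequences. The level of 250×10⁹/L is a dosing threshold inside the protocol's normal range, and a high platelet count is not itself an AESI. All of this stands, and it is why the point is minor. It does not supply the number of subjects above the threshold, and it does not bring unscheduled counts into a table.

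Three stronger readings are tempting, and the documents do not support them.

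- A reader might infer that Protocol 9.5 and 10, which speak of laboratory assessments in both phases, contradict the single central panel in Table 8. They do not. Protocol 9.5 defers to Tables 7 and 8, and neither Protocol 10 nor the safety endpoint promises a frequency.
- A reader might infer that SAP 4.5 is what empties the whole Extension laboratory summary. It does so for platelets only. Chemistry and the other hematology parameters are sparse because Table 8 schedules them so, and changing SAP 4.5 would fill none of those cells.
- A reader might multiply 72 subjects by 24 visits and call 1,728 the maximum number of local counts left out. That product covers scheduled monthly visits at the planned sample size. Enrollment is at least 72, weekly and twice-weekly counts come on top, and no Extension entry rate is given.

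It can also be said that the SAP already places early-termination samples, since SAP 4.2 assigns End of Study records to a visit by study day and Table 7 combines the two visit types. That is a fair reading, and its use in the Extension needs only to be confirmed.

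**Conclusion.** The point holds as a minor defect of the safety analysis plan. The rule in SAP 4.5 leaves the safety summary of platelet count with 0 of 24 scheduled monthly counts after E-1, and with 3 of 12 on-treatment weekly counts in the Core Phase. No planned table reports how many subjects exceeded 250×10⁹/L. The figure of 24 assumes a subject who completes the Extension. Early-termination samples may add some central values, in a number that the documents do not give.

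Two wording points go with it. SAP 7.5.3 promises a by-visit Extension laboratory summary without saying that scheduled data exist only at E-1. Protocol 9.5 says that platelet count analyses use local results and makes no exception for safety, whereas Protocol 11.2.2 and SAP 4.5 assign central counts to the safety assessment.

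No efficacy result, dose or clinical threshold is affected.

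**What to change.** - **SAP 4.5 and 7.5.3:** admit recorded local platelet counts, scheduled and unscheduled, to one descriptive safety table per phase. It should give the maximum post-baseline count, and the number and percentage of subjects with any count above 250×10⁹/L. Present it by treatment received in the Core Phase, and by cohort and overall in the Extension. Keep central results for all other parameters.
- **SAP 7.5.3:** state that the Extension chemistry and hematology summary covers E-1 and any early-termination samples, as scheduled, and confirm that the study-day rule in SAP 4.2 places the latter.
- **Platelet source:** reconcile the wording of Protocol 9.5 with Protocol 11.2.2 and SAP 4.5.

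The cost is SAP wording, a clarification of the protocol text, and two descriptive tables from data already collected. No new sampling and no alpha are needed. The downside is that counts from different local laboratories are pooled, which the efficacy analysis already does.
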